8 STUDY COMPLETION AND POST-STUDY TREATMENT / MEDICAL CARE

8.1 Study completion

A subject who has received study treatment and completed the follow-up period is considered to have completed the study.

8.2 Premature withdrawal from study

Subjects may voluntarily withdraw from the study without justification for any reason at any time. Subjects are considered withdrawn if they state an intention to withdraw from further participation in all components of the study (i.e., withdrawal of consent), if they die, or are lost to follow-up. If a subject withdraws consent, no further data will be collected in the CRF from the date of withdrawal onward. The investigator may withdraw a subject from the study (without regard to the subject's consent) if, on balance, he/she believes that continued participation in the study would be contrary to the best interests of the subject. Withdrawal from the study may also result from a decision by the sponsor for any reason, including premature termination or suspension of the study.

Subjects are considered as lost to follow-up if all reasonable attempts by the investigator to communicate with the individual failed. The site must take preventive measures to avoid a subject being lost to follow-up (e.g., document different ways of contact such as telephone number, home address, email address, person to be contacted if the subject cannot be reached). If the subject cannot be reached, the site must make a reasonable effort to contact the subject, document all attempts, and enter the loss of follow-up information into the CRF. The following methods must be used: at least 3 telephone calls must be placed to the last available telephone number and one registered letter must be sent by post to the last available home address. Additional methods may be acceptable if they are compliant with local rules/regulations (e.g., a visit by site personnel to the subject's home), respecting the subject's right to privacy. If the subject is still unreachable after all contact attempts listed above, he/she will be considered to be lost to follow-up.

If premature withdrawal occurs for any reason, the reason (if known) for premature withdrawal from the study, along with who made the decision (subject, investigator, or sponsor personnel), must be recorded in the CRF, if known.

If, for whatever reason (except death or loss-to-follow-up), a subject is withdrawn from the study, the investigator should make efforts to schedule a last appointment / telephone call to assess the safety and wellbeing of the subject. Data obtained during this last appointment / telephone call will be recorded in the subject's medical records but it will not be collected in the CRF. The investigator must provide follow-up medical care for all

subjects who are prematurely withdrawn from the study, or must refer them for appropriate ongoing care, as described in Section 8.4.

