9.1.4 Reporting of adverse events

All AEs with an onset date after signing of informed consent and up to 30 days after study treatment administration must be recorded on specific AE pages of the CRF.

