9.2.2 Reporting of serious adverse events

All SAEs occurring after signing of informed consent up to 30 days after study treatment administration must be reported on AE pages in the CRF and on a SAE form, regardless of the investigator-attributed causal relationship with study treatment or study-mandated procedures.

An SAE is defined as related to protocol-mandated procedures if it appears to have a reasonable possibility of a causal relationship to either the study design or to protocol-mandated procedures (e.g., discontinuation of a subject's previous treatment during a washout period leading to exacerbation of underlying disease).

All SAEs must be reported by the investigator to the sponsor's Global Drug Safety department within 24 hours of the investigator's first knowledge of the event.

All SAEs must be recorded on a SAE form, irrespective of the study treatment received by the subject, and whether or not this event is considered by the investigator to be related to study treatment.

The SAE forms must be sent to the sponsor's Global Drug Safety department (contact details are provided on the SAE form). The investigator must complete the SAE form in English, and must assess the event's causal relationship to the study treatment.

Any relevant information from source documents regarding the SAE, e.g., hospital notes or discharge summaries, etc., must be summarized on the SAE form.

Follow-up information about a previously reported SAE must also be reported within 24 hours of receiving it. The sponsor's Global Drug Safety personnel may contact the investigator to obtain further information.

If the subject is hospitalized in a hospital other than the study site, it is the investigator's responsibility to contact this hospital to obtain all SAE-relevant information and documentation.

The expectedness of an adverse reaction is determined by the sponsor in the reference safety information (RSI) section provided in the most recent version of the IB. Any SAE that is assessed as related and unexpected against the RSI is known as a SUSAR and must be reported by the sponsor/delegate to concerned HAs (including the EudraVigilance database if the study is conducted in Europe), IECs/IRBs and investigators.

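### Protocol 8.2 keeps adverse events first reported or updated at a withdrawn subject's last safety contact out of the CRF, in conflict with the 30-day recording rule in 9.1.4 and 9.2.2

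*Protocol*

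**What the plan says.** Protocol 8.2 contains two rules about data after withdrawal.

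- **Consent withdrawn.** "If a subject withdraws consent, no further data will be collected in the CRF from the date of withdrawal onward".
- **Last contact.** The trigger is broader: "If, for whatever reason (except death or loss-to-follow-up), a subject is withdrawn from the study". A final appointment or call to check on the subject's safety should then be attempted, and its findings are dealt with as follows: "Data obtained during this last appointment / telephone call will be recorded in the subject's medical records but it will not be collected in the CRF".

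Section 8.2 also lets the investigator end participation without the subject asking for it: "The investigator may withdraw a subject from the study (without regard to the subject's consent) if, on balance", the investigator thinks staying in would be against the subject's interests. It also lets the sponsor withdraw subjects for any reason.

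The reporting sections set a rule with no exception for withdrawn subjects. Protocol 9.1.4, for the AE pages of the CRF: "All AEs with an onset date after signing of informed consent and up to 30 days after study treatment administration must be recorded". Protocol 9.2.2: "All SAEs occurring after signing of informed consent up to 30 days after study treatment administration must be reported on AE pages in the CRF". Each SAE also needs an SAE form, which goes to the sponsor's drug safety department within 24 hours.

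**The concern.** A rule of no further CRF data is understandable for a subject who withdraws consent. Protocol 8.2 applies a similar bar to the findings of a contact held specifically to assess safety, and does so by reference to withdrawal for any reason. A site that learns at that contact of an AE with onset inside the 30 days cannot comply with both 8.2 and 9.1.4.

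What is at stake is the completeness of the AE tables. By the protocol's own account (1.5.1) this is the first study of the drug in patients, and bleeding is the main known risk of the class. A non-serious bleed has no reporting route other than the CRF.

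**Working it through.** No calculation decides this point. The check is to set the passages side by side.

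1. **Whom the last-contact rule covers.** It excepts only death and loss to follow-up, where no contact is possible. That leaves consent withdrawal, investigator withdrawal and sponsor withdrawal. Consent withdrawal already has its own sentence in 8.2, so the practical addition is the other two groups, in which consent may still stand.

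2. **What 9.1.4 and 9.2.2 require of those groups.** Both run from consent to 30 days after dosing and neither mentions withdrawn subjects. Where the protocol wants information kept out of the CRF, it says so in the reporting section itself: 9.1.5 and 9.2.3 do this for follow-up information obtained after the End-of-Study call. Protocol 11.1 also requires a CRF for subjects who do not complete the study. The reporting sections therefore contain nothing that yields to 8.2.

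3. **Whether an event outside the CRF can reach the analysis.** Protocol 10.2.3.1 and SAP 7.2.1.1 define an AE for analysis as an event on the AE module of the CRF. SAP 7.2.1.6 identifies an SAE by the investigator's entry in the eCRF. A dosed subject belongs to the Safety set whether or not withdrawn (Protocol 10.1.5, SAP 4.1.5). An event left off the module is therefore missing from the numerator, while its subject stays in the denominator.

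4. **Which outputs are touched.**
   - An event that began within 48 h of dosing but is first mentioned at the last contact is missed as treatment-emergent (Protocol 10.2.3.1, SAP 7.2.1.2).
   - A later event is missed from the non-treatment-emergent columns of SAP Table 5, which include haemorrhage. All AEs and SAEs up to End-of-Study are a listed safety endpoint (Protocol 6.3).
   - An update can matter too. SAP 7.2.1.4 uses the worst reported severity, so a worsening disclosed only at that contact would not be reflected.

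5. **What is not touched.** The bar concerns data obtained at the last contact. It does not remove an AE already recorded. Protocol 8.2 itself requires the reason for withdrawal, if known, and who decided it to be entered in the CRF. The SAE form is separate from the CRF, so the 24-hour route to drug safety stays open.

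6. **Size.** The documents give no rate of investigator or sponsor withdrawal after dosing, and no rate of AEs first disclosed at a last contact. The only nearby figure, about 10% in Protocol 10.5, is drop-out or non-evaluable data for the primary pharmacodynamic endpoint and measures something else. As a pure assumption, if 1% to 5% of the 324 planned subjects were withdrawn after dosing for all reasons together, that would be 0.01 × 324 ≈ 3 to 0.05 × 324 ≈ 16 subjects. Consent withdrawals, where the bar is not disputed, are included in that range, and only some of the remainder would have an event to report. It is not an estimate of missing events.

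**The case against.** The strongest reply is that little is exposed.

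- An AE that prompts withdrawal comes before withdrawal, so 9.1.4 already requires it in the CRF.
- SAEs have their own route to the sponsor.
- The drug is given once. After the Day 2 visit only the End-of-Study call remains, so there is little left from which to withdraw a subject.
- The AE summaries listed in Protocol 10.3.4.1 are all treatment-emergent, with a 48 h window.
- The wording of 8.2 is also open to a narrower reading. It first describes withdrawn subjects as those who withdraw consent, die or are lost. Excepting the last two leaves consent withdrawal, for which a CRF bar is a deliberate choice.

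The first three points stand and set the limits of the finding. The fourth stands for the protocol's list, but the SAP also tabulates events from the follow-up period, and a late-disclosed early event is still treatment-emergent. On the fifth, 8.2 goes on to name investigator and sponsor withdrawal before it sets the last-contact rule for withdrawal whatever the reason, so the wider reading is the natural one. If the narrower one was meant, the text should say so.

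A reader might go further and infer three things that the documents do not support.

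- **That AEs in subjects withdrawn for safety reasons are lost.** Events recorded before withdrawal are kept, SAEs still reach drug safety, and the last-contact findings remain in the medical records.
- **That withdrawn subjects are analysed as event-free.** This is true only of a subject with no AE recorded earlier.
- **That AE or bleeding rates are biased downward by a known amount.** No document says that investigator withdrawals after dosing are mostly for safety. Any calculation of how one missed bleed among the 216 subjects planned for active drug (2 × 108) would move a confidence bound presupposes a missed event that nothing in the documents establishes.

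**Conclusion.** The inconsistency is real and worth correcting. Followed as written, 8.2 keeps out of the CRF, and so out of the AE tables, any event with onset within 30 days of dosing that is first reported or updated at the last contact of a subject withdrawn by the investigator or sponsor. In practice this chiefly means non-serious events.

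The number affected cannot be estimated from the documents and may well be small. The primary pharmacodynamic analysis is unaffected. The conclusion assumes that the last-contact rule means what it says about the reason for withdrawal, and that the subjects concerned have not also withdrawn consent. It does not depend on any assumed withdrawal rate.

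**What to change.** Reconcile 8.2 with 9.1.4 and 9.2.2 in a protocol amendment:

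- In 8.2, limit the bar on CRF collection to subjects who withdraw consent to further data collection.
- State that, for subjects withdrawn by the investigator or the sponsor, any AE or SAE with onset up to 30 days after dosing that is learned at the last appointment or call is entered in the CRF.

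This is about two sentences. It uses a contact that 8.2 already asks sites to attempt, and it adds no visit, procedure or follow-up beyond that contact. The downside is a few more CRF entries.

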8.3 Premature termination or suspension of the study

The sponsor reserves the right to terminate the study at any time globally or locally. Investigators can terminate the participation of their site in the study at any time.

If a study is prematurely suspended or terminated, the sponsor/delegate will promptly inform the investigators, the IECs/IRBs, and HAs, as appropriate, and provide the reasons for the suspension or termination.

If the study is suspended or prematurely terminated for any reason, the investigator — in agreement with the sponsor — must promptly inform all enrolled subjects and ensure their appropriate treatment and follow-up, as described in Section 8.4. The sponsor/delegate may inform the investigator of additional procedures to be followed in order to ensure that adequate consideration is given to the protection of the subjects' interests.

In addition, if the investigator suspends or terminates a study without prior agreement from the sponsor, the investigator must promptly inform sponsor personnel and the IEC/IRB, and provide both with a detailed written explanation of the termination or suspension.

If the IEC/IRB suspends or terminates its approval / favorable opinion of a study, the investigator must promptly notify sponsor personnel and provide a detailed written explanation of the termination or suspension.

8.4 Medical care of subjects after study completion / withdrawal from study

The subject's standard of care will not be affected by study participation. For this PK/PD and safety study, subjects will receive 1 single administration of study treatment on top of their standard of care.

9 SAFETY DEFINITIONS AND REPORTING REQUIREMENTS

9.1 Adverse events

9.1.1 Definition of adverse events

An AE is any untoward medical occurrence, i.e., any unfavorable and unintended sign, including an abnormal laboratory finding, symptom, or disease that occurs in a subject during the course of the study, whether or not considered by the investigator as related to study treatment.

A TEAE is any AE temporally associated with the use of study treatment until 48 h after study treatment administration whether or not considered by the investigator as related to

study treatment. The 48-h window for TEAEs has been defined to include at least 5 half-lives of ACT-246475.

AEs include:

- Exacerbation of a pre-existing disease.
- Increase in frequency or intensity of a pre-existing episodic disease or medical condition.
- Disease or medical condition detected or diagnosed during the course of the study even though it may have been present prior to the start of the study.
- Continuous persistent disease or symptoms present at study start that worsen following the signing of informed consent.
- Abnormal assessments, e.g., change on physical examination, ECG findings, if they represent a clinically significant finding that was not present at study start or worsened during the course of the study.
- Laboratory test abnormalities if they represent a clinically significant finding, symptomatic or not, which was not present at study start or worsened during the course of the study.

Overdose, misuse, abuse of the study treatment and study treatment errors will be reported as an AE.

9.1.2 Intensity of adverse events

The intensity of clinical AEs is graded on a 3-point scale (mild, moderate, severe) and is reported on specific AE pages of the CRF.

All changes in intensity of an AE during the study will be reported in the CRF.

The three categories of intensity are defined as follows:

Mild

The event may be noticeable to the subject. It does not usually influence daily activities, and normally does not require intervention.

Moderate

The event may make the subject uncomfortable. Performance of daily activities may be influenced, and intervention may be needed.

Severe

The event may cause noticeable discomfort, and usually interferes with daily activities. The subject may not be able to continue in the study, and treatment or intervention is usually needed.

A mild, moderate, or severe AE may or may not be serious [see Section 9.2.1]. These terms are used to describe the intensity of a specific event. Medical judgment should be used on a case-by-case basis.

Seriousness, rather than intensity assessment, determines the regulatory reporting obligations.

9.1.3 Relationship to study treatment

Each AE must be assessed by the investigator as to whether or not there is a reasonable possibility of causal relationship to the study treatment, and reported as either related or unrelated. The determination of the likelihood that the study treatment caused the AE will be provided by the investigator.

9.1.4 Reporting of adverse events

All AEs with an onset date after signing of informed consent and up to 30 days after study treatment administration must be recorded on specific AE pages of the CRF.

9.1.5 Follow-up of adverse events

AEs still ongoing more than 30 days after study treatment administration must be followed up until they are no longer considered clinically relevant or until stabilization. The follow-up information obtained after the subject's EOS telephone call will not be collected by the sponsor.

9.2 Serious adverse events

9.2.1 Definitions of serious adverse events

An SAE is defined by the ICH guidelines as any AE fulfilling at least one of the following criteria:

- Fatal.
- Life-threatening: Refers to an event in which the subject was at risk of death at the time of the event. It does not refer to an event that hypothetically might have caused death had it been more severe.
- Requiring in-patient hospitalization or prolongation of existing hospitalization.
- Resulting in persistent or significant disability or incapacity.
- Congenital anomaly or birth defect.

- Medically significant: Refers to important medical events that may not immediately result in death, be life-threatening, or require hospitalization but may be considered to be SAEs when, based upon appropriate medical judgment, they may jeopardize the subject, and may require medical or surgical intervention to prevent one of the outcomes listed in the definitions above.

The following reasons for hospitalization are not considered as SAEs:

- Hospitalization for cosmetic elective surgery, or social and/or convenience reasons (including hospitalization related to protocol procedures).
- Hospitalization for pre-planned (i.e., planned prior to signing informed consent) surgery or standard monitoring of a pre-existing disease or medical condition that did not worsen, e.g., hospitalization for coronary angiography in a subject with stable angina pectoris.

However, complications that occur during hospitalization are AEs or SAEs (e.g., if a complication prolongs hospitalization).

9.2.2 Reporting of serious adverse events

All SAEs occurring after signing of informed consent up to 30 days after study treatment administration must be reported on AE pages in the CRF and on a SAE form, regardless of the investigator-attributed causal relationship with study treatment or study-mandated procedures.

An SAE is defined as related to protocol-mandated procedures if it appears to have a reasonable possibility of a causal relationship to either the study design or to protocol-mandated procedures (e.g., discontinuation of a subject's previous treatment during a washout period leading to exacerbation of underlying disease).

All SAEs must be reported by the investigator to the sponsor's Global Drug Safety department within 24 hours of the investigator's first knowledge of the event.

All SAEs must be recorded on a SAE form, irrespective of the study treatment received by the subject, and whether or not this event is considered by the investigator to be related to study treatment.

The SAE forms must be sent to the sponsor's Global Drug Safety department (contact details are provided on the SAE form). The investigator must complete the SAE form in English, and must assess the event's causal relationship to the study treatment.

Any relevant information from source documents regarding the SAE, e.g., hospital notes or discharge summaries, etc., must be summarized on the SAE form.

Follow-up information about a previously reported SAE must also be reported within 24 hours of receiving it. The sponsor's Global Drug Safety personnel may contact the investigator to obtain further information.

If the subject is hospitalized in a hospital other than the study site, it is the investigator's responsibility to contact this hospital to obtain all SAE-relevant information and documentation.

The expectedness of an adverse reaction is determined by the sponsor in the reference safety information (RSI) section provided in the most recent version of the IB. Any SAE that is assessed as related and unexpected against the RSI is known as a SUSAR and must be reported by the sponsor/delegate to concerned HAs (including the EudraVigilance database if the study is conducted in Europe), IECs/IRBs and investigators.

9.2.3 Follow-up of serious adverse events

SAEs still ongoing more than 30 days after study treatment administration must be followed up until resolution or stabilization, or until the event outcome is provided. The follow-up information obtained after the subject's EOS telephone call must be reported to the sponsor's Global Drug Safety department, but it is not recorded in the CRF.

9.2.4 After the 30-day follow-up period

New SAEs occurring after the 30-day follow-up period must be reported to the sponsor's Global Drug Safety department within 24 hours of the investigator's knowledge of the event, **only** if considered by the investigator to be causally related to previous exposure to the study treatment.

9.3 Pregnancy

If a woman becomes pregnant during study participation, the investigator must counsel the subject and discuss the risks of continuing with the pregnancy and the possible effects on the fetus.

9.3.1 Reporting of pregnancy

Any pregnancy occurring after study start (i.e., signing of informed consent) up to 30 days following study treatment administration must be reported within 24 hours of the investigator's knowledge of the event.

Pregnancies must be reported on the Pregnancy form, which is faxed to the sponsor's Global Drug Safety department (see contact details provided on the Pregnancy form), and on an AE page in the CRF.

